2.2. Research Methods and Design

This study tests a hypothesis that a single session of psilocybin (the 'medication dosing' session) in the context of pre- and post-dose psychotherapy will result in improvement of symptoms of depression and burnout measured 4 weeks post-dose. This study hypothesis will be tested in a single site, double-blind, randomized controlled design involving 30 clinician participants that will compare effects of a single 25mg oral dose of psilocybin to a 100 mg of niacin (active placebo). The primary outcome measurements will be collected 4 weeks after

Page 16 Version 1.16, July 18, 2022

the psilocybin dose, after which the participant group assignment will be unblinded, and participants who received niacin will be offered the opportunity to have a second dose session with a 25 mg dose (with pre- and post-dose psychotherapy).

Precautions will be taken to reduce potential for COVID exposure, following FDA guidance (https://www.fda.gov/media/136238/download):

- Some psychotherapy sessions can be conducted by video, although at least one preparation session and one integration session will be done in person.
- COVID-19 screening procedures mandated by UW Medicine will be followed per UW Medicine policy. Currently UW Medicine policies require a basic symptom check before ambulatory care encounters, for example.
- Participants will be tested for COVID using a rapid antigen test on the morning
 of their medication session, and therapists will also be tested on the morning of
 the participant's medication session.
- Physical distancing will be maintained as much as possible.

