3.1. Research Procedures

Participants will complete self-report and clinician-administered measures at baseline, prior to the medication dosing session, and at designated study visits (see figure next page).

Schedule for Activities during Randomized Phase									
Purpose	Screen	Prep	Prep	Medi- cation	Inte- gration	Inte- gration	Inte- gation	Follow -up	
Study day (approx)	-21-14	-7	-1	0	1	8	15	28	
Visit number		V1	V2	V3	V4	V5	V6	V7	
Research activity									
Demographics	X								
Eligibility Determination	X								
Medical exam	X								
Informed consent	X								
Caregiver contact info	X								
Blood draw	X								
Pregnancy screen (if applicable)	X			Х					
PI review of inclusion/exclusion	Х								

Page 18 Version 1.16, July 18, 2022

Informed Consent		X						
Mental health evaluation		Х						
Education re expectations	Х	Х						
Preparation psychotherapy		Х						
Urine screen	Χ							
Randomization				Х				
Medication (psilocybin or control)				Х				
Medication dosing monitoring				Х				
Integration psychotherapy					Х	Х	Х	
Adverse event reporting				Х	Х	Х	Х	
Un-blinding								X**
Measures								
Mont-Asberg Depression (MADRS)	Х	Х			Х	Х		Х
Beck Depression Scale		Х			X	Х		Х
Stanford Fulfillment Index		Х			X	Х		Х
Post-traumatic stress (PCL5)		Х			Х	Х		Х
Likelihood to leave job		Х			Х	Х		Х
Self-reported mystical exp				Х				
Moral injury symptom scale		Х						Х
Psychedelic Music Questionnaire					Х			
Psychological flexibility (AAQII)		Х				Х		Х
Interoceptive awareness (MAIA2)		Х			Х	Х		Х
Suicidality (C-SSRS)	Х	Х	Х	Х	Х	Х	Х	Х
Qualitative interview								Х
Adverse events, Suicidality	Х	Х	Χ	Х	X	Х	Х	Х

^{**}The unblinding will be done after the study coordinator has verified that the Day 28 measures have been completed.

Follow up measures for participants randomized to psilocybin							
Durance	Follow	Follow	Follow				
Purpose	-up	-up	-up				
Study day (approx.)	56	84	180				
Visit number	V8	V9	V10				
Measures							
Mont-Asberg Depression (MADRS)	Х	Х	Х				
Beck Depression Scale	Х	Х	Х				
Stanford Fulfillment Index	Χ	Х	Х				
Post-traumatic stress (PCL5)	Χ	Х	Х				
Likelihood to leave job	Χ	Х	Х				
Psychological flexibility (AAQII)	Χ	Х	X				
Interoceptive awareness (MAIA2)	Χ	Х	X				
Suicidality (C-SSRS)	Χ	X	X				
Qualitative interview							
Adverse events	Χ	Х	X				

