6.1. Randomization Blinded Study Phase

Upon completion of the Preparation sessions, participants will be assigned to one of the two conditions for the Medication Dosing session: the experimental condition (synthesized psilocybin 25mg) or placebo (niacin). The randomization will be performed by IDS and capsules will be placed in envelopes for each participant. Randomization will be stratified by profession (physician vs nurse) and ethnicity (Black or Hispanic vs other).

Psilocybin and niacin will be administered in identically appearing opaque, size 0 gelatin capsule with approximately 180ml of water. The dose of psilocybin will be 25 mg and the niacin will be 100 mg. Each participant will have the option of participating in the medication dosing sessions. In the study, half of the participants will be randomized to receive psilocybin (n=15) or the placebo, niacin (n=15). Following the first treatment session of either the active agent or placebo, participants who were randomized to receive placebo will be offered the option to receive open-label psilocybin. (The blind will be broken at 4weeks to make this determination, after primary endpoint measures have been collected. Clinical raters will remain blind to the treatment assignment). Data will be collected from all subjects after open-label treatment for descriptive purposes, but these data will not be analyzed as part of our primary analysis plan.

The participant's condition assignment will be maintained from randomization until the 4 week unblinding. If there is an adverse event or other emergency requiring knowledge of participant's condition assignment, as when pharmacological intervention is necessary, the blind may be broken for an individual participant. In this case, the study raters who will administer the questionnaires will remain blind to the participant's condition assignment.

Participants in the placebo condition will be eligible for an open-label study continuation. They will be re-screened after the blind is broken to make sure they still meet study criteria. If they are eligible and choose to enroll in the open-label continuation, they may do so, undergoing psilocybin-assisted sessions occurring within another seven to 14-day period.

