Findings of pregnancy, active cardiac medical issues, abnormal liver function, abnormal renal function, or abnormal blood counts, and any lab indicating an undiagnosed illness would exclude a participant from moving on to the preparation 1 visit. When screening requirements have been met, participants will have a visit with the PI and/or key study personnel in which the study, the scheduling and the procedures will be reviewed. All participants' questions will be answered prior to obtaining an informed consent.

After providing informed consent, the participant will complete initial measures. Note that randomization to the psilocybin or control (niacin) treatment groups will occur at the end of visit 2.

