6.2.3. Medication Dosing session (Visit 3)

Procedures for psilocybin administration and the conduct of the session will be similar to procedures used in studies with psilocybin conducted at New York University, Johns Hopkins, and Yale. Participants will be instructed to consume a low-fat breakfast before reporting to the clinic room for the psilocybin sessions. Before psilocybin administration, urine pregnancy test will be conducted in females of childbearing potential, and a negative pregnancy test will be required in order to continue in the medication session. Participants and staff will also complete pre-session questionnaires. Before each psilocybin session, study personnel will interview the participant. If the investigator believes that the session is contraindicated, the session will be cancelled or postponed.

Psilocybin will be administered in opaque gelatin capsules with approximately 100 ml water. At least one therapist, under the supervision of the investigators, will be present in the room and available to respond to participants' physical and emotional needs during the full course of the session (at least 7 hours). A physician on the study team will be immediately available via pager or mobile phone for at least 3 hours or until the peak effects of psilocybin have subsided, whichever is longer.

During the session, participants will lie on a couch, wear eyeshades, and listen to a program of music through headphones. The participant will be encouraged to focus her or his attention inward. The eyeshades and music are intended to encourage this inward reflection. Heart rate and blood pressure will be measured pre drug administration, at 30, 60, 90, 120 minutes after drug administration, and then at least hourly until at least 6 hours after drug administration and until drug effects have subsided. Heart rate and blood pressure assessments will be obtained after the participant has been sitting or recumbent for at least 5 minutes. Sessions are expected to last approximately 7 to 10 hours. A sample schedule for the medication dosing session is as follows:

Approximate Time	Procedure or Action
09:00	Urine pregnancy test for females of childbearing potential,
	participant acclimates to environment, completes measures.
09:30	Baseline BP, Pulse, Temp.
	Medication Administration.
	Begin video recording.
10:00	BP, Pulse
10:30	BP, Pulse
11:00	BP, Pulse
11:30	BP, Pulse
12:30	BP, Pulse
13:30	BP, Pulse
14:30	BP, Pulse
15:30	BP, Pulse
16:30	BP Pulse.

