	Assessment for discharge home.

At about the same time of each heart rate/blood pressure measurement, monitors will complete notations in the Medication Day Case Report Form to rate the presence and intensity of behaviors, signs, and reported symptoms, including sleepiness, amount of speech, anxiety, stimulation/arousal,

tearing/crying, nausea/vomiting, yawning, restlessness, feelings of unreality, visual changes, euphoria, and peacefulness. Video and audio recordings will be made throughout the session, as allowed by participants.

Participants will be encouraged to lie comfortably in bed wearing eye shades during the first few hours of the experience and to listen to pre-selected music chosen by the study staff. Two team members will remain with the participants the entire time and beavailable for any processing of intrapsychic material made manifest by the treatment.

If participants experience or report on any adverse effects or if the research staff feelsthat at the end of testing, that the participant has any adverse effects, participants will be asked / required to remain until effects wear off and medically cleared by the PI. Medical assistance will be offered. The investigators will query participants about suicidal ideation or intent during screening, and prior to each psilocybin session. Participants who evidence suicidal ideation or intent will be withdrawn from the study and referred to appropriate psychiatric care.

In the event that participants experience distressing anxious symptoms during the drug session, the clinical personnel in attendance (the principal investigator and team member) will initiate verbal communication designed to reorient and reassure that participant. The occurrence and intensity of anxiety or panic responses can be reduced through providing participants with information on potential drug effects, supervision, and monitoring of participants for the duration of drug effects. The goal in this study is to treat participants undergoing anxiety or panic reactions first by verbal and psychological interventions and using anxiolytic medication only after verbal and psychological interventions have failed, and if participants are endangering themselves or others. Residual symptoms will be addressed during the frequent follow-up psychotherapy visits with the investigators.

At the end of the medication dosing session:

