9.2. Statistical approach

The primary objective of this randomized trial is to compare the mean change from baseline MADRS among patients randomized to receive psilocybin to that among patients randomized to receive niacin. The time point of primary interest at which change will be assessed will be 4 weeks. Mean change between the two groups will be assessed with the two-sample t-test, or the Wilcoxon rank-sum test if distributional assumptions for the t-test are violated. The table below shows the minimum detectable assumed-true effect size (represented in standard-deviation units, or the difference in mean change divided by the common standard deviation) to observe a statistically significant difference (at the two-sided significance level of .05) with 80% and 90% power for a variety of total sample sizes.

Sample size	80% Power	90% Power
N=30	1.06 SD units	1.23 SD units
N=40	0.91 SD units	1.05 SD units
N=50	0.81 SD units	0.94 SD units

Based on the values in the above table, we will randomize 30 patients, as we hypothesize that an assumed-true effect size of 1.06 – 1.23 is achievable based on previous studies by [name] and Davis and achieved effect sizes of 1.46 at 2 weeks at 1.69 at 6 weeks¹⁹ or 2.2 at 5 weeks.¹⁸ A sample size of N=30 will provide >90% power to detect a significant difference in the primary outcome between the psilocybin 25 mg vs niacin groups. Assuming a 15% drop-out rate of subjects in this study, we will enroll 36 subjects and assume 6 will not complete the study, so full enrollment in this study will be 36 with a target of 30 subjects completing the study.

The primary analysis will be done using the intent-to-treat principle. Randomization will be done using a permuted block design with randomly selected block sizes.

Key secondary endpoints include those listed below, and a hierarchical approach will be taken to the potential analysis of these endpoints. If the primary endpoint is statistically significant, then these secondary endpoints will be (potentially) formally compared in a hierarchical manner in the order listed below.

- 1. Mean change in burnout (Stanford Fulfillment index) from baseline to 4 weeks between the two groups
- 2. Mean change in symptoms of PTSD (PCL5) from baseline to 1 week and 4 weeks between the two groups.

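### Randomisation is placed at the end of visit 2 in the text but at visit 3 in the schedule; the earlier point lets people who are never dosed enter the intent-to-treat set without a 4-week MADRS.

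*Combined protocol and SAP*

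**What the plan says.** The combined protocol and SAP times randomisation in three places.

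- Section 6.2.1: "randomization to the psilocybin or control (niacin) treatment groups will occur at the end of visit 2". Visit 2 is the second preparation visit, about Day -1 in the schedule.
- Section 6.1: "Upon completion of the Preparation sessions, participants will be assigned to one of the two conditions for the Medication Dosing session". This names no visit or day but is compatible with the end of visit 2.
- Section 3.1, table headed "Schedule for Activities during Randomized Phase": the mark in the randomisation row is under V3, Day 0, the same column as the medication row.

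Four things happen on Day 0 before the capsule is given.

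- Pregnancy test, where applicable (6.2.3): "a negative pregnancy test will be required in order to continue in the medication session".
- Pre-session interview (6.2.3): "If the investigator believes that the session is contraindicated, the session will be cancelled or postponed".
- Query about suicidal ideation or intent before each session (6.2.3): "Participants who evidence suicidal ideation or intent will be withdrawn from the study and referred to appropriate psychiatric care".
- COVID test (2.2): "Participants will be tested for COVID using a rapid antigen test on the morning" of the session. The consequence of a positive result is not stated.

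On analysis, section 9.2 says: "The primary analysis will be done using the intent-to-treat principle". It neither defines that set nor says how a randomised but undosed participant is handled. The primary MADRS is timed at 4 weeks after the dosing session (1.1.1, 2.2; Day 28 in the schedule).

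**The concern.** The end of visit 2 and the moment of dosing are separated by checks that can end participation. If allocation comes first, a person stopped by a check counts as randomised. In the usual all-randomised sense of intent-to-treat, that person belongs in the primary analysis but has no dosing date from which to count 4 weeks. The t-test or Wilcoxon test of change in section 9.2 needs an observed value, and no missing-data method is given. Site staff following the text and staff following the schedule could therefore randomise at different points, and the handling of undosed people might be settled only after the fact. At stake is avoidable loss of primary data in a trial that plans 15 per arm.

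**Working it through.** **Reading the schedule.** The columns run Screen, V1 (Day -7), V2 (Day -1), V3 (Day 0), and so on. The randomisation and medication rows each carry one mark, both in the fourth column. Two rows agreeing in position make a text-extraction fault unlikely. Text and table therefore name different visits on different days.

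**Who is affected if allocation is at the end of visit 2.**

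| Day-0 event | Dosed? | 4-week date? |
|---|---|---|
| Positive pregnancy test | No | No |
| Session cancelled after interview | No | No |
| Withdrawn for suicidality | No | No |
| Session postponed | Yes, later | Yes, later |
| Positive COVID test | Not stated | Not stated |

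**Power inputs (section 9.2).** Two-sided alpha 0.05; effect 1.06 to 1.23 SD; both 30 randomised and 36 enrolled with 30 completing are stated. The number failing Day-0 checks is not in the documents. I assume 2 or 3, which is about 5-10% of 30.

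**Formula.** For a two-sample t-test with arms n1 and n2: ν = n1 + n2 − 2, δ = d × √(n1·n2/(n1+n2)), and power = P(|T| > t(0.975, ν)), where T is noncentral t with ν degrees of freedom and noncentrality δ.

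**Reproducing the plan.** With 15 per arm and d = 1.06, δ = 1.06 × √7.5 = 2.903, ν = 28, critical value 2.048, power 80.0%. With d = 1.23, δ = 3.368 and power is 90.2%. Solving for d gives 1.060 and 1.226 SD, matching the N=30 row. Enrolment: 30/(1 − 0.15) = 35.3, rounded up to 36, which also matches.

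**Undosed participants with no 4-week value.**

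| Randomised | Lost | Arms | δ at 1.06 SD | Power at 1.06 SD | Power at 1.23 SD |
|---|---|---|---|---|---|
| 30 | 0 | 15/15 | 2.903 | 80.0% | 90.2% |
| 30 | 2 | 14/14 | 2.804 | 77.0% | 87.9% |
| 30 | 3 | 14/13 | 2.752 | 75.3% | 86.6% |
| 36 | 0 | 18/18 | 3.180 | 87.1% | 94.8% |
| 36 | 2 | 17/17 | 3.090 | 85.0% | 93.5% |
| 36 | 3 | 17/16 | 3.043 | 83.8% | 92.8% |

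If 36 are randomised, it takes 6 losses to return to 15 per arm and 80.0%.

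**Undosed participants assessed anyway.** Suppose they are measured at 4 weeks from the planned date, have no treatment effect and are spread evenly over the arms. The mean difference then shrinks by the factor 1 − k/N. With 30 randomised and k = 3, the effect is 1.06 × 0.9 = 0.954 SD and power is 71.3%; with k = 2, it is 74.4%. With 36 randomised, the figures are 80.8% (k = 3) and 83.1% (k = 2). Assessing these people keeps the randomised comparison intact but does not recover power.

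**The case against.** The strongest reply is that this is a clerical mismatch with little behind it. Sections 6.1 and 6.2.1 agree, and the only dissent is one mark in a table. The main points of that reply fare as follows.

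- *The two placements need not give different analysis sets.* A reader might infer that they do. The schedule names a visit, not an order within it, so allocating at V3 before the morning checks gives the same set as the end of visit 2. This stands: the sets differ only if V3 allocation follows the checks, and the fix must say so.
- *Not every check stops dosing.* A reader might take all four Day-0 checks as routes out of the trial. The documents do not support that: a postponed session still gives a dose and a clock, and no consequence is attached to a positive COVID test. This stands, and three routes remain. Earlier pregnancy screening, and the C-SSRS at screening, V1 and V2, should also make late failures less common.
- *No bias.* A reader might suspect that post-randomisation exclusions distort the comparison. Allocation is double-blind and no dose has yet been given, so the checks cannot depend on arm. This stands: the harm is mainly to precision.
- *The enrolment allowance covers it.* If 36 are randomised, 2-3 losses leave power above 80% at 1.06 SD. This stands in part. Section 9.2 says both that 30 will be randomised and that 36 will be enrolled, so whether the allowance applies after randomisation is itself unclear. It is also meant for all dropout, not only Day-0 failures.
- *Pharmacy lead time.* The product is a compounded, tightly controlled drug, and allocation at the end of visit 2 gives the pharmacy notice. This is a real cost and is the reason for the fallback in the fix.

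**Conclusion.** The contradiction is in current text and has to be reconciled. Following section 6.2.1 places anyone stopped before dosing in the intent-to-treat set with no dose-anchored 4-week MADRS and no stated handling. The effect is modest. With 30 randomised and no value for the undosed, power at 1.06 SD falls from 80% to 77% (2 lost) or 75% (3 lost), and at 1.23 SD from 90% to 88% or 87%. With 36 randomised, 2-3 losses leave about 84-85% at 1.06 SD. These figures rest on an assumed failure count, near-even losses over the arms and the plan's own effect sizes. The documents do not support a claim of bias or of a seriously underpowered trial. The point is worth correcting because the loss is avoidable and the remedy is cheap.

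**What to change.** State in sections 6.1 and 6.2.1 and in the schedule that allocation is made on Day 0, after all existing pre-dose checks are passed and immediately before dosing. Define the intent-to-treat set in section 9.2 as all participants so randomised. The checks themselves do not change.

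The cost is wording, plus same-day release of the allocated capsule by the investigational pharmacy, within the profession-by-ethnicity strata. Section 6.1 already has the pharmacy randomise and place capsules in envelopes, so the added burden is timing and having stock ready for each stratum.

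If same-day release is not workable, keep the end of visit 2, correct the schedule to match, and assess randomised but undosed participants at 4 weeks from the planned dosing date. This gives them a defined primary assessment, at the price of the dilution shown in the working.

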6.2.2. Preparation visits (Visits 1, 2)

Preparation for the medication dosing session (psilocybin or control) consists of 2 meetings for a total of 5-6 hours in the 2 weeks before the medication dosing session. The main purpose of the preparation meetings is to develop rapport and trust, which helps minimize the risk of fear or anxiety reactions during the psilocybin sessions. Additional meetings and contact hours will be scheduled if it is judged necessary to establish rapport and trust. Consistent with other published psilocybin protocols, the participant's life history and current situation in life will be reviewed, and intentions and expectations for the psilocybin sessions will be discussed. Audio or video recordings (with coded id number) of this session will be made to allow the participant and the investigator-therapists to review preparation sessions.

6.2.3. Medication Dosing session (Visit 3)

Procedures for psilocybin administration and the conduct of the session will be similar to procedures used in studies with psilocybin conducted at New York University, Johns Hopkins, and Yale. Participants will be instructed to consume a low-fat breakfast before reporting to the clinic room for the psilocybin sessions. Before psilocybin administration, urine pregnancy test will be conducted in females of childbearing potential, and a negative pregnancy test will be required in order to continue in the medication session. Participants and staff will also complete pre-session questionnaires. Before each psilocybin session, study personnel will interview the participant. If the investigator believes that the session is contraindicated, the session will be cancelled or postponed.

Psilocybin will be administered in opaque gelatin capsules with approximately 100 ml water. At least one therapist, under the supervision of the investigators, will be present in the room and available to respond to participants' physical and emotional needs during the full course of the session (at least 7 hours). A physician on the study team will be immediately available via pager or mobile phone for at least 3 hours or until the peak effects of psilocybin have subsided, whichever is longer.

During the session, participants will lie on a couch, wear eyeshades, and listen to a program of music through headphones. The participant will be encouraged to focus her or his attention inward. The eyeshades and music are intended to encourage this inward reflection. Heart rate and blood pressure will be measured pre drug administration, at 30, 60, 90, 120 minutes after drug administration, and then at least hourly until at least 6 hours after drug administration and until drug effects have subsided. Heart rate and blood pressure assessments will be obtained after the participant has been sitting or recumbent for at least 5 minutes. Sessions are expected to last approximately 7 to 10 hours. A sample schedule for the medication dosing session is as follows:

Approximate Time	Procedure or Action
09:00	Urine pregnancy test for females of childbearing potential,
	participant acclimates to environment, completes measures.
09:30	Baseline BP, Pulse, Temp.
	Medication Administration.
	Begin video recording.
10:00	BP, Pulse
10:30	BP, Pulse
11:00	BP, Pulse
11:30	BP, Pulse
12:30	BP, Pulse
13:30	BP, Pulse
14:30	BP, Pulse
15:30	BP, Pulse
16:30	BP Pulse.
	Assessment for discharge home.

At about the same time of each heart rate/blood pressure measurement, monitors will complete notations in the Medication Day Case Report Form to rate the presence and intensity of behaviors, signs, and reported symptoms, including sleepiness, amount of speech, anxiety, stimulation/arousal,

tearing/crying, nausea/vomiting, yawning, restlessness, feelings of unreality, visual changes, euphoria, and peacefulness. Video and audio recordings will be made throughout the session, as allowed by participants.

Participants will be encouraged to lie comfortably in bed wearing eye shades during the first few hours of the experience and to listen to pre-selected music chosen by the study staff. Two team members will remain with the participants the entire time and beavailable for any processing of intrapsychic material made manifest by the treatment.

If participants experience or report on any adverse effects or if the research staff feelsthat at the end of testing, that the participant has any adverse effects, participants will be asked / required to remain until effects wear off and medically cleared by the PI. Medical assistance will be offered. The investigators will query participants about suicidal ideation or intent during screening, and prior to each psilocybin session. Participants who evidence suicidal ideation or intent will be withdrawn from the study and referred to appropriate psychiatric care.

In the event that participants experience distressing anxious symptoms during the drug session, the clinical personnel in attendance (the principal investigator and team member) will initiate verbal communication designed to reorient and reassure that participant. The occurrence and intensity of anxiety or panic responses can be reduced through providing participants with information on potential drug effects, supervision, and monitoring of participants for the duration of drug effects. The goal in this study is to treat participants undergoing anxiety or panic reactions first by verbal and psychological interventions and using anxiolytic medication only after verbal and psychological interventions have failed, and if participants are endangering themselves or others. Residual symptoms will be addressed during the frequent follow-up psychotherapy visits with the investigators.

At the end of the medication dosing session:

- Participants will complete paper or computer-based questionnaires designed to assess acute subjective experiences associated with the medication dosing session.
- Study therapists will the participant's mood and suicidality with the C-SSRS.
- Participants will also be asked to write a narrative description of the experience of the psilocybin session before their next in-person meeting.
- Participants will remain under observation until both the participant and investigator agree that their perception, cognition, functioning, and judgment are no longer impaired by the medication.
- Participants will be discharged in the company of the adult who is providing continuous contact.

